9.4.4 Safety Endpoints

Safety will be assessed through descriptive summaries of the endpoints listed in [Table 7](#).

9.4.5 Other Analyses

9.4.5.1 Summaries of Conduct of Study

The number of participants who enroll, discontinue, or complete the study will be summarized by study arm. Reasons for premature study withdrawal and study treatment discontinuation will be listed and summarized. Intercurrent events will be listed and summarized. Enrollment and major protocol deviations will be listed and evaluated for their potential effects on the interpretation of study results.

9.4.5.2 Summaries of Demographics and Baseline Characteristics

Demographics and baseline characteristics (including age, sex, race, *APOE* ϵ 4 status) will be summarized by study arm. The baseline value will be defined as the last available value recorded prior to the initiation of study treatment. Descriptive statistics (mean, standard deviation, median, and range) will be presented for continuous variables and counts and percentages will be presented for categorical variables.

9.4.5.3 Pharmacokinetic Analyses

Plasma concentration data for gantenerumab will be tabulated and summarized. Descriptive summary statistics will include the arithmetic mean, median, range, standard deviation, and CV, as appropriate. Because a sparse PK sampling design is being used, population (nonlinear mixed-effects) modeling will be used to analyze the dose concentration-time data of gantenerumab. Information from other clinical studies may be incorporated to establish the PK model. The selection of parameters and the derivation of individual measures of exposure, such as area under the concentration-time curve (AUC), C_{max} , and trough concentration, will depend on the final PK model used for this analysis. The results of this modeling analysis may be reported separately in the Clinical Study Report.

Cerebrospinal fluid concentrations of gantenerumab will be tabulated and summarized as appropriate.

The influence of background medication on the pharmacokinetics of gantenerumab will be explored and, if appropriate, concentration-effect relationships may be assessed post-hoc for PD, efficacy, immunogenicity or safety measures.

Additional PK analyses will be conducted as appropriate and may be reported separately in the CSR.

9.4.5.4 Immunogenicity Analyses

The numbers and proportions of ADA-positive participants and ADA-negative participants at baseline (baseline prevalence) and after drug administration (post-baseline incidence) will be summarized for participants exposed to gantenerumab. When determining post-baseline incidence, participants are considered to be ADA-positive if they are ADA-negative or have missing data at baseline but develop an ADA response following study drug exposure (treatment-induced ADA response), or if they are ADA-positive at baseline and the titer of 1 or more post-baseline samples is at least 4-fold higher in comparison to the titer at the baseline (treatment-enhanced ADA response). Participants are considered to be ADA-negative if they are ADA-negative or have missing data at baseline and all post-baseline samples are negative, or if they are ADA-positive at baseline but do not have any post-baseline samples with a titer that is at least 4-fold greater than the titer of the baseline sample (treatment-unaffected ADA response).

The relationship between ADA status and safety, efficacy, pharmacokinetics, and biomarker endpoints may be analyzed and reported via descriptive statistics.

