6. STUDY TREATMENT(S) AND CONCOMITANT THERAPY

Study treatment is defined as any investigational treatment, marketed product, placebo, or medical device intended to be administered to a study participant according to the study protocol.

The term 'study drug' in Study WN42444 refers to gantenerumab or placebo. Gantenerumab and placebo are also designated as investigational medicinal products (IMPs). According to E.U. guidance, the PET tracers, as used in the context of this study, are designated as non-IMPs. In some regions, according to local regulations, these PET tracers may be considered to be IMPs (see Section 6.1.3).

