6.3.2 Blinding

The study is to be conducted in a double-blinded manner to minimize potential bias from investigators and participants. The Sponsor, participants and their study partners, and the site staff will remain blinded to treatment assigned at randomization, even after a participant *progresses to MCI or dementia due to AD* and starts active treatment. In order to protect study blinding, no one administering or with the potential to administer drug to participants will be permitted to conduct any efficacy assessments. Study partners will only be permitted to support 1 participant in the trial *and may not be enrolled as study participants at the same time*.

The Master Randomization or Master Medication List will not be available at the study center to Roche monitors, Roche project statisticians, or to the project team at Roche. Unblinding should not occur except in the case of emergency situations where knowledge of the study drug assigned would affect participant care. The investigator should make every effort to contact the Medical Monitor before unblinding a participant. If unblinding is necessary for participant management, the investigator will be able to break the treatment code by contacting the IxRS. The investigator should document and provide an explanation for any premature unblinding (e.g., accidental unblinding, unblinding due to a serious adverse event). Any request from the investigator for information about the treatment administered to study participants for another purpose must be discussed with the Medical Monitor.

While PK and immunogenicity samples must be collected from participants not exposed to gantenerumab to maintain the blinding of treatment assignment, PK and ADA assay results for such participants are generally not needed for the safe conduct or proper interpretation of the study data. Laboratories responsible for performing study drug PK and ADA assays will be unblinded to participant treatment assignments to identify appropriate samples for analysis. Pharmacokinetic and ADA samples from participants

not exposed to gantenerumab will not be analyzed for study drug PK concentration or ADAs except by request (e.g., to evaluate a possible error in dosing).

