8.8 IMMUNOGENICITY ASSESSMENTS

Antibodies to gantenerumab will be evaluated in plasma samples collected from all participants according to the schedule of activities (see Section 1.3). Additionally, plasma samples should also be collected at the final visit from participants who discontinued study treatment or were withdrawn from the study. These samples will be tested by the Sponsor or Sponsor's designee.

Plasma samples will be screened for antibodies binding to gantenerumab and the titer of confirmed positive samples will be reported.

All samples collected for detection of antibodies to study treatment will also be evaluated for gantenerumab plasma concentration to enable interpretation of the antibody data. Samples may be stored for a maximum of 5 years (or according to local regulations) after the final Clinical Study report has been completed at a facility selected by the Sponsor to enable further analysis of immune responses to gantenerumab.

Remaining volumes from these samples may also be used for further characterization of potential immune responses and for any gantenerumab-related exploratory analyses or assay development/validation experiments.

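### For control participants who switch to gantenerumab, the ADA rule sets baseline before placebo, so some ADA that predates gantenerumab is classed as treatment-induced

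*Combined protocol and SAP*

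**What the plan says.** Five parts of the protocol bear on this.

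- **The ADA rule (9.4.5.4).** Baseline prevalence and post-baseline incidence "will be summarized for participants exposed to gantenerumab". A participant is treatment-induced positive if they are "ADA-negative or have missing data at baseline but develop an ADA response following study drug exposure". A participant who is positive at baseline counts only if a later titer is at least four times the baseline titer.
- **Baseline (9.4.5.2).** "The baseline value will be defined as the last available value recorded prior to the initiation of study treatment". No other section defines baseline.
- **Study treatment and study drug (Section 6).** "Study treatment is defined as any investigational treatment, marketed product, placebo, or medical device intended to be administered to a study participant". The term study drug "refers to gantenerumab or placebo".
- **The switch (4.1.2 and 4.1.3; Tables 3 and 6).** Control participants with adjudicated progression who are on target dose move to gantenerumab, unless the ongoing Phase III studies in early AD fail to show efficacy. Both post-progression schedules have an ADA sample at Week 1P, marked as taken before dosing. Nothing makes that sample a baseline.
- **Which samples are assayed (6.3.2 and 8.8).** Section 6.3.2 says PK and ADA samples from participants "not exposed to gantenerumab will not be analyzed for study drug PK concentration or ADAs except by request". Section 8.8 says: "Antibodies to gantenerumab will be evaluated in plasma samples collected from all participants according to the schedule of activities". Neither addresses the placebo-period samples of a control participant who is exposed later.

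**The concern.** An ADA result is attributable to gantenerumab only if it is judged against a sample taken just before gantenerumab. For the gantenerumab arm, the Week 1 sample does this. For a control switcher, the definitions place the baseline at Week 1, and the period counted as exposure then includes all the time on placebo, which can run to several years.

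The presence of ADA relative to baseline is a secondary safety endpoint (Table 7). ADA status also feeds the exploratory relationships with efficacy, safety, PD and PK. If some switchers carry a treatment-induced label that gantenerumab cannot have caused, reported incidence is too high and the ADA-positive group is mixed, and this falls on participants who have just progressed.

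**Working it through.** The plan states no ADA figure to reproduce, so the main check is a trace through the definitions.

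**1. Trace for a control switcher**

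- Study treatment includes placebo, so baseline is the Week 1 sample taken before the first placebo dose.
- Once switched, the participant is exposed to gantenerumab and enters the summary in 9.4.5.4.
- Study drug includes placebo, so every sample after Week 1, including pre-dose Week 1P, follows study drug exposure and is post-baseline.

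**2. Outcome by what is assayed**

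| Assayed before the switch | Week 1 result | ADA before gantenerumab | Class under the rule |
|---|---|---|---|
| All scheduled samples | Negative | Positive at any sample up to Week 1P | Treatment-induced |
| Week 1 and Week 1P only | Negative | Positive at Week 1P | Treatment-induced |
| None | Missing | Present, first detected after the switch | Treatment-induced |
| Week 1 at least | Positive | Already present at Week 1 | Baseline-positive; counts only with a four-fold titer rise |

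The first three rows are wrong for a gantenerumab incidence. The fourth is not affected: ADA already present at Week 1 does not become treatment-induced.

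**3. How many samples are involved if all are assayed**

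From Tables 1 to 6, the ADA samples after Week 1 are at Weeks 13, 25, 37, 53, 79, 105, 131, 157 and 183, then Week 1P. With k samples before gantenerumab and an assumed per-sample positive rate p, taking samples as independent, the chance of at least one positive is 1 − (1 − p)^k.

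| Last regular sample before the switch | k (including 1P) | p = 0.5% | p = 1% | p = 2% |
|---|---|---|---|---|
| Week 53 | 5 | 2.5% | 4.9% | 9.6% |
| Week 105 | 7 | 3.4% | 6.8% | 13.2% |
| Week 183 | 10 | 4.9% | 9.6% | 18.3% |

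The documents give no value for p and nothing to support independence. These are conditional illustrations for switchers only.

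**4. Size in the pooled exposed population**

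Assume all 600 gantenerumab-arm participants are exposed, a share w of the 600 controls switches, and a share s of switchers has ADA before gantenerumab but is negative or missing at Week 1. Misclassified participants = 600 × w × s. As a share of all exposed this is 600ws / (600 + 600w).

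| w (assumed) | Exposed | Misclassified at s = 1% / 5% / 10% | Share of exposed |
|---|---|---|---|
| 10% (60) | 660 | 0.6 / 3 / 6 | 0.09% / 0.45% / 0.91% |
| 20% (120) | 720 | 1.2 / 6 / 12 | 0.17% / 0.83% / 1.67% |
| 30% (180) | 780 | 1.8 / 9 / 18 | 0.23% / 1.15% / 2.31% |

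**5. Size among switchers**

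If true induction is t, the rule reports s + (1 − s)t. With an assumed t = 5% and s = 1%, 5% or 10%, that is 5.95%, 9.75% or 14.5%.

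**The case against.** The case on the other side has five parts.

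- **The baseline definition is borrowed.** It sits under demographics and baseline characteristics, and 9.4.5.4 sets none of its own. Because that section concerns participants exposed to gantenerumab, its mention of drug administration could be read as gantenerumab. This shows ambiguity, but the operative clause says study drug, a term that Section 6 defines to include placebo, and there is no other baseline definition to fall back on.
- **The SAP prevails (Section 9) and could set a switcher-specific baseline.** True. No separate SAP is in the text reviewed. However, 9.4.5.4 already gives a full algorithm and, unlike the confirmatory secondary endpoints and the imputation rules, does not defer it to the SAP.
- **The laboratory could assay the right samples.** ADA laboratories are unblinded to select samples, and 8.8 allows storage for up to 5 years after the final report. Once a control participant switches, the exemption in 6.3.2 need not apply. Assaying Week 1 removes the error for ADA already present then. It does not help a switcher who is negative at Week 1 and positive at Week 1P, because Week 1P still counts as post-baseline.
- **The rates may be too high.** Section 8.8 reports confirmed positives, Appendix 3 calls the immunogenic risk low for a fully human antibody, and background reactivity may persist within a person, so independent samples overstate accumulation. This stands and is why no single figure is claimed.
- **Little hangs on it.** Safety endpoints are summarized descriptively (9.4.4), the ADA relationships are exploratory, and the problem arises only if the switch is active. This also stands.

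**Conclusion.** The point holds in a limited form. With the switch active, the definitions as written class two kinds of result in control switchers as treatment-induced when gantenerumab cannot have caused them: ADA first appearing after Week 1 but before gantenerumab, and pre-existing ADA when Week 1 is missing or unassayed. On assumed inputs (10% to 30% of controls switching, 1% to 10% of them affected) this is about 1 to 18 participants, or 0.1 to 2.3 percentage points of the pooled exposed population. The true size depends on a background rate that the documents do not give.

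A reader might infer three stronger things that the documents do not support.

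- **That all ADA present before gantenerumab is called treatment-induced.** It is not: an assayed positive Week 1 sample makes the participant baseline-positive, under the four-fold rule.
- **That reported immunogenicity would be inflated by 7% to 10%.** The 6.8% and 9.6% figures apply to switchers only, assume a 1% rate and independent samples, and need every placebo-period sample to be assayed, which 6.3.2 leaves open.
- **That a primary or confirmatory result is at risk.** The ADA summary carries no hypothesis test.

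It is worth correcting because a stated rule misclassifies and the sample needed is already scheduled.

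**What to change.** In 9.4.5.4:

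- Define ADA baseline as the last sample before the first gantenerumab dose: Week 1 for the gantenerumab arm and pre-dose Week 1P for control switchers.
- Count only samples after that dose as post-baseline.
- In the treatment-induced clause, refer to exposure to gantenerumab rather than to study drug.

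In 6.3.2, state that each control switcher's pre-dose Week 1P sample is assayed for ADA once the participant is exposed, consistent with 8.8. If a separate SAP repeats the rule, make the same change there, since it prevails.

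The cost is a few sentences and one assay per switcher. No visit or blood draw is added: Tables 3 and 6 already schedule the sample, and their footnote that waives some Week 1P assessments done within the previous 4 weeks does not list ADA. The assay laboratories are already unblinded, so the change does not affect the study blind.

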9.5 INTERIM ANALYSIS

9.5.1 Optional Interim Analysis

Based on availability of information pertaining to gantenerumab or other compounds with a similar mode of action that may emerge during the course of this study, the Sponsor may choose to conduct an interim analysis once participants have completed at least 2 years of treatment.

An independent data coordinating center will be responsible for the interim analysis and study results will only be reviewed by the iDMC. The Sponsor will remain blinded. Interactions between the iDMC and Sponsor will be carried out as specified in the iDMC Charter. Details of the interim analysis, including the decision to conduct the optional interim analysis, the rationale, timing, and statistical details for the analysis (such as the data that would be reviewed by the iDMC and futility or efficacy thresholds) will be documented in the SAP, and the SAP will be submitted to relevant health authorities as required at least 2 months prior to conducting the interim analysis.

9.6 INDEPENDENT DATA MONITORING COMMITTEE

A formal iDMC will be used for this study. The iDMC will be unblinded and evaluate participant safety and select efficacy on a regular basis. In addition to the data defined in the iDMC Charter (e.g., the incidence, severity, and nature of adverse events, serious adverse events, ARIA-E and ARIA-H, ISRs, adverse events of special interest, and the MMSE), the iDMC will review all necessary cumulative data at regular intervals during the study, including further efficacy data when needed.

The frequency of these assessments is specified in the iDMC Charter. At the time of each review, the iDMC will make appropriate recommendations (e.g., the study should continue as planned, enrollment in a specific arm should be discontinued, the treatment regimen should be modified, the protocol should be amended, and enrollment should be held pending further safety evaluations). The iDMC will also evaluate planned or unplanned interim analyses for efficacy or futility.

Decisions will be made in consideration of the totality of the available data.

Ad-hoc meetings may be called in addition to scheduled meetings, as necessary, to provide recommendations on management of any new safety issues.

Specific operational details such as the committee's composition, frequency and timing of meetings, and members' roles and responsibilities are detailed in the iDMC Charter.

Final decisions will rest with the Sponsor.

REFERENCES

Appendix 1 Regulatory, Ethical, and Study Oversight Considerations

TABLE OF CONTENTS

- A1-1. Regulatory and Ethical Considerations
- A1-2. Financial Disclosure
- A1-3. Informed Consent Process
- A1-4. Data Protection
- A1-5. Administrative Structure
- A1-6. Dissemination of Clinical Study Data
- A1-7. Data Quality Assurance
- A1-8. Source Documents
- A1-9. Study and Site Closure
- A1-10. Publication Policy
- A1-11. Protocol Deviations

A1–1. REGULATORY AND ETHICAL CONSIDERATIONS

This study will be conducted in accordance with the protocol and with the following:

- Consensus ethical principles derived from international guidelines, including the Declaration of Helsinki and Council for International Organizations of Medical Sciences international ethical guidelines
- Applicable International Council for Harmonisation (ICH) Guideline for Good Clinical Practice (GCP)
- Applicable laws and regulations

The protocol, Informed Consent Form (ICF), Investigator's Brochure, and other relevant documents (e.g., advertisements) must be submitted to an Institutional Review Board (IRB) or Ethics Committee (EC) by the investigator and reviewed and approved by the IRB/EC before the study is initiated.

Any substantial amendments to the protocol will require IRB/EC and health authority approval (as locally required) before implementation of changes, with the exception of administrative changes or changes necessary to eliminate an immediate hazard to study participants.

The investigator will be responsible for the following:

- Providing written summaries of the status of the study to the IRB/EC annually or more frequently in accordance with the requirements, policies, and procedures established by the IRB/EC
- Notifying the IRB/EC of serious adverse events or other significant safety findings, as required by IRB/EC procedures
- Providing oversight of the conduct of the study at the site and ensuring adherence to requirements of 21 Code of Federal Regulations (CFR; U.S. sites only), the ICH Guideline for GCP, the IRB/EC, Regulation (E.U.) No. 536/2014 (E.U. sites only), and all other applicable local regulations

A1–2. FINANCIAL DISCLOSURE

Investigators will provide the Sponsor with sufficient, accurate financial information in accordance with local regulations to allow the Sponsor to submit complete and accurate financial certification or disclosure statements to the appropriate health authorities. Investigators are responsible for providing information on financial interests during the study and for 1 year after completion of the study (see definition of end of study in Section 4.4).

Appendix 1: Regulatory, Ethical, and Study Oversight Considerations

A1-3. INFORMED CONSENT PROCESS

This section relates to the informed consent process for the optional blood-based biomarker (BBBM) prescreening and the main study.

Participation in the optional BBBM prescreening requires signing of a separate BBBM prescreening ICF. The investigator or authorized designee will explain the nature of the optional BBBM prescreening to the participant and answer all questions regarding the optional BBBM prescreening.

For participation in the main study, the investigator or authorized designee will explain the nature of the study to the participant, to the participant's study partner, and to the participant's postdose observer(s) (if applicable). The investigator or authorized designee will also answer all questions regarding study participation during the informed consent process for the Main Participant, Study Partner, Postdose Observer, and Mobile Nursing ICFs.

Participants, the participant's study partner, and the participant's postdose observer(s) must be informed that their participation is voluntary. The participant, the participant's study partner, and the participant's postdose observer(s) will be required to sign a statement of informed consent that meets the requirements of 21 CFR 50 (U.S. sites only), the ICH Guideline for GCP, and the IRB/EC.

The medical record must include a statement that written informed consent was obtained before the participant, the participant's study partner, and the participant's post-dose observer(s) were enrolled in the study and the date the written consent was obtained. The authorized person obtaining the informed consent must also sign the ICF.

If any of the ICFs are revised (through an amendment or an addendum) to communicate information that may affect a participant's, participant's study partner's, or the participant's postdose observer(s)' willingness to continue in the study, the participant, the participant's study partner, or the participant's postdose observer(s) must re-consent by signing the most current version of the ICF or the addendum, in accordance with applicable laws and IRB/EC policy.

A copy of each ICF must be provided to the participant, the participant's study partner and the participant's postdose observer(s). A participant who is rescreened is not required to sign another ICF if the rescreening occurs within 90 days from the previous ICF signature date.

The BBBM prescreening ICF and the Main Participant ICF will each contain a separate section that addresses the use of remaining mandatory samples for optional exploratory research. The investigator or authorized designee will explain to each participant the

